infection or death, is 5 days or 28 days. The **administrative censoring date** is the earlier of the cut-date of the dataset, or randomization date plus analysis time period.

Comment: The notion of "administrative censoring" is important in time-to-event analyses in the presence of competing risks. For example, the Fine-Gray method for estimating the sub-hazard ratio for sustained recovery can be approximated by using a Cox proportional hazards model where follow-up time for participants who died prior to achieving sustained recovery is not censored at death, but at the administrative censoring date.

Censoring for time-to-event analyses

For interim analyses, the type of censoring used will depend on the data collection schedule.

- If the reporting of the endpoint is data-driven (e.g., SAEs and deaths are reported as they occur), then follow-up is censored at the administrative censoring date, at the date of withdrawal, or loss to follow-up, whichever occurs earliest.
- If the date of the event is elicited retrospectively at fixed study visits spaced more than one week apart (e.g., "sustained recovery"), follow-up will be censored at the last day the endpoint status was ascertained.
- Sensitivity analyses will be provided for key analyses when the outcome status is uncertain.

For **final** analyses, follow-up will be censored on the last day the outcome status was ascertained.

Adverse events (AEs) will be classified by system organ class according to MedDRA®¹ (currently version 24.1 [September 2021] is used; when new versions are implemented, items are recoded). AEs will be graded according to the *DAIDS Table for Grading the Severity of Adult and Pediatric Adverse Events, Corrected Version 2.1 (July 2017)* (also referred to as the *DAIDS AE Grading Table*).⁷ Cause of death will also be coded according to MedDRA®.

The number and percent of participants with grade 1-4 AEs will be summarized by day and grade, and by MedDRA® System Organ Class and grade. The percentage of participants with AEs will be compared between treatment groups according to grade cut-offs, e.g., "percent of participants with any AE", "percent of participants with grade 2 or higher AEs", etc., using CMH tests. The total number of events and median (IQR) of events per participant will also be summarized.

Additionally, the incidence of grade 3 and higher AEs will be summarized (number and percent of participants), and compared between treatment groups using time-to-event methods.

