Comment: For investigational agents that are administered as a one-time infusion, such as nMAbs, the composite outcome at Day 5 is the primary measure to assess safety while the trial is still enrolling, as described in the protocol. This safety outcome and other safety outcomes through Day 28 will be considered along with the ordinal outcomes at Day 5 at interim data reviews by the DSMB to assess futility. When a trial is unblinded after the Day 90 follow-up is completed, however, treatment comparisons through Day 90 provide a more comprehensive evaluation of the investigational agent. For the publication of the main results for a specific agent, "time to death" and the composite of "death, SAE, clinical organ failure, or serious infections" through Day 90 would usually be presented as the main safety analyses, along with other safety outcomes. This decision will be agent-specific, and will be specified prior to the unblinding of the data for the agent.

• All-cause mortality through follow-up will be analyzed using time-to-event methods. Cumulative proportions of participants who died in each treatment group will be estimated using Kaplan-Meier estimates, and summarized in tables (proportion of participants who died by Days 5, 7, 14, 28, 60, 90, month 6, 12, and 18) and figures (Kaplan-Meier curves with pointwise 95% CIs). Treatment groups will be compared for time to death using log-rank tests, stratified by study site pharmacy and disease severity, and an overall HR will be

estimated with 95% CIs using stratified Cox proportional hazards models. Two other analyses will also be carried out to investigate the pattern of mortality differences, if any, between the treatment groups: 1) the proportional hazards assumption will be investigated; and 2) hazard ratios during the first 28 days of follow-up versus after 28 days will be estimated and compared.

- Cause of death will be MedDRA® coded and summarized by treatment group.
- The following composite endpoints will be analyzed using time-to-event methods (cumulative proportions of participants with events will be estimated using Kaplan-Meier curves with pointwise 95% CIs; treatment groups will be compared using log-rank tests; numbers and percent of participants with events will be summarized by treatment group, and overall HRs with 95% CI will be estimated using Cox proportional hazards models):

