- Participants who are alive but have not experienced sustained recovery will be censored at the last date the endpoint status was ascertained (for interim analyses as well as the final analysis).
- For interim monitoring, two sensitivity analyses will be performed:
 - 1. Follow-up for time to sustained recovery will be censored *administratively* at the cut-date for the current report or Day 90, whichever comes first, with last known endpoint status carried forward. For participants who died, this type of censoring is integrated into Gray's test; using a log-rank test would require carrying forward the "not recovered" status for participants who died, up to the administrative censoring date.

2. Administrative censoring as described above will be applied, with the modification that participants who have been discharged from the hospital, were "home" at the latest date when residence was ascertained (but for < 14 days), and, if they have remained there, would have been at home for 14+ days by the cut-date, will be imputed as having experienced *sustained recovery* (achieved on day 14 at home).

Participants who withdrew consent or were lost to follow-up will be censored at the date of withdrawal or the last date the endpoint status was known, respectively.

In the first sensitivity analysis, the "not recovered" status is carried forward to the administrative censoring date; in the second analysis, "sustained recovery" is assumed at the earliest possible date. The first analysis potentially underestimates the rate of recovery, whereas the second analysis overestimates the recovery rate. In all analyses for time to sustained recovery, death is treated as competing risk.

Ascertainment of sustained recovery

The date of discharge from the index hospital will be recorded. Irrespective of the timing of the hospital discharge, there will be patient contact approximately every two weeks, on Days 14, 28, 42, 60, 75, and 90, either at a scheduled clinic visit or through phone contact. At these time points, a) vital status, and b) the location of the participant over time will be recorded, to assess whether the participant had been "at home" for 14 days. Therefore, the outcome status of sustained recovery will usually be ascertained within 3 weeks or less of the date the outcome was achieved.

• To illustrate the status of the primary endpoint, the recovery status of participants will be described over time with the following categories (at interim reviews):

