Data completeness and study conduct reports will be provided by treatment group (for the closed report) and pooled across treatment groups (for the open report). Data summaries for the infusion of the investigational agent on Day 0 are described in Section 6; several of those reports are also relevant for monitoring study conduct and will be included in the open report or provided to study leadership, pooled across treatment groups.

The following data summaries will be provided to assess data completeness and study conduct:

- Number and percent of participants with protocol deviations, and type of protocol deviation
- Expected and observed number (% of expected) of participants who completed visits on Days 1-7, 14, 28, 42, 60, 75, and 90.
- Expected and observed number (% of expected) of participants with known outcome status for the pulmonary and the pulmonary+ outcomes on Day 5.
- Ascertainment of the primary outcome: Expected and observed number (% of expected) of
 participants with known status of "time to sustained recovery" at days 28, 60, and 90. To
 ascertain "sustained recovery", several elements are required: vital status; the status of
 hospitalization; if discharged, the status of the residence ("home" versus other).
- Expected and observed number (% of expected) of participants with known vital status at days 5, 14, 28, 60 and 90, and at months 6, 12, and 18.

- Number and percent of participants who withdrew consent or were lost to follow-up (no contact and unknown vital status for 45+ days).
- If substantial numbers of participants are lost to follow-up (e.g., more than 10% of participants), Kaplan-Meier estimates for the cumulative proportion of participants who are lost to follow-up over time, by treatment group, will be provided (closed report only).
- Listing of participants who withdrew consent, including dates of randomization, pulmonarycategory at baseline, receipt of study treatment, date of withdrawal, and reason of withdrawal.
- Length of follow-up: Median, IQR, range
- Collection of specimens: Expected and observed number (% of expected) of participants with specimens collected as specified by the protocol, by visit.
- Expected and observed numbers of participants with local laboratory data at baseline and on Day 5.

A visit counts as "expected" if the visit window has closed or the data have been received.

12 SARS-CoV-2 Antibody, Antigen, and Viral RNA Levels

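### The 45-day definition of loss to follow-up in SAP section 11 does not fit the contact schedule after Day 90, so it over-counts losses there and leaves interim censoring of late deaths unclear

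*SAP*

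**What the plan says.** **Definition.** SAP section 11 lists among its completeness summaries the "Number and percent of participants who withdrew consent or were lost to follow-up (no contact and unknown vital status for 45+ days"). The list is introduced by "The following data summaries will be provided to assess data completeness and study conduct". The definition carries no time limit. If many are lost (more than 10% is the example given), Kaplan-Meier estimates of loss over time by arm go into the closed report.

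**Schedule.** Section 8.1 states that "there will be patient contact approximately every two weeks, on Days 14, 28, 42, 60, 75, and 90". After that, section 11 counts participants with "known vital status at days 5, 14, 28, 60 and 90, and at months 6, 12, and 18". Table D-1 in Appendix D allows 14 days either side at months 6, 12 and 18, and up to 10 days late at Day 90. Section 1.2 limits data collection after Day 90 to hospitalizations and deaths.

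**Censoring.** For interim analyses of endpoints reported as they occur, with deaths named as an example, section 3 says "follow-up is censored at the administrative censoring date, at the date of withdrawal, or loss to follow-up, whichever occurs earliest". Final analyses are censored on the last day the outcome status was ascertained.

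**Analyses past Day 90.** Section 7 tabulates the "proportion of participants who died by Days 5, 7, 14, 28, 60, 90, month 6, 12, and 18" and analyses re-admission or death through 18 months. Section 9.1 includes time to death through 18 months among the subgroup outcomes.

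**The concern.** A threshold for time without contact has to exceed the longest gap that a compliant participant can have. Here it does so only through Day 90. At a data cut between later contacts, people who have missed nothing can be reported as lost. The count then mixes true attrition with the calendar.

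The second stake is conditional. Section 3 uses loss to follow-up as an interim censoring event without defining it, and the section 11 wording is the only operational definition in the SAP. If a programmer applies it, survivors between contacts leave the risk set while deaths in the same interval are still counted because they are reported as they occur. Censoring would then depend on the outcome, and estimated late mortality would be biased upward.

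**Working it through.** **1. Gaps between planned contacts.** Inputs are the visit days and windows in Table D-1, with a month taken as 365.25/12 days (month 6 = Day 182.6). The longest allowed gap runs from an on-time visit to the latest next visit. The shortest runs from the latest visit to the earliest next one.

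| Interval | Nominal (days) | Shortest | Longest |
|---|---|---|---|
| Day 42 to 60 | 18 | 15 | 23 |
| Day 75 to 90 | 15 | 10 | 100 − 75 = 25 |
| Day 90 to month 6 | 92.6 | 182.6 − 14 − 100 = 68.6 | 182.6 + 14 − 90 = 106.6 |
| Month 6 to 12 | 182.6 | 182.6 − 28 = 154.6 | 182.6 + 28 = 210.6 |
| Month 12 to 18 | 182.6 | 154.6 | 210.6 |

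From Day 7 to Day 90 no allowed gap exceeds 25 days, so an on-schedule participant never reaches 45. After Day 90 every allowed gap exceeds 45, even the shortest.

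**2. Share of time flagged.** With nominal visit days 90, 183, 365 and 548, and no contact or vital-status information in between:

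(183 − 90 − 45) + (365 − 183 − 45) + (548 − 365 − 45) = 48 + 137 + 138 = 323 days.

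323 / (548 − 90) = 323/458 = 71%. By interval this is about 51% of the first gap and 75% of each later one. The flag clears at the next completed contact.

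**3. Illustration of the conditional bias.** None of these inputs is in the documents; all are assumptions. The base case has 440 participants alive at Day 90, follow-up at the cut uniform on Days 100 to 250, no true loss, a death hazard of 0.00025 per day, and all deaths up to the cut known.

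- Share labelled lost: cuts on Days 135–183 and 228–250 qualify, (48 + 22)/150 = 47% before removing deaths. The simulation gives 46%.
- True mortality from Day 90 to Day 180: 1 − exp(−0.00025 × 90) = 2.2%. Administrative censoring recovers it.
- Flagged survivors censored at last planned contact: Kaplan-Meier 3.2%, about 45% too high.
- Flagged survivors censored 45 days after last contact: 2.65%, about 19% too high.

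**4. Sensitivity.**

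- Hazards from 0.0001 to 0.0005 per day barely change the relative bias.
- With censoring at last contact, cuts spread over Days 100–300 give about 28%, and cuts over Days 100–200 more than double the estimate.
- If all follow-up at the cut lies between Days 90 and 135, or between Days 200 and 225, nobody is flagged and the bias is zero.

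**5. Treatment comparison.** In the base case, with flagged survivors censored at last contact, log-rank rejection under the null is 5.2%, against 5.4% with administrative censoring. With a true hazard ratio of 2.0, the mean log hazard ratio is 0.692 against 0.696. Absolute mortality is inflated about equally in both arms.

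**The case against.** A reader might infer that on-schedule participants are classed as lost and censored, so that the trial's mortality result is biased. The documents do not support that.

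- **The definition is a reporting item.** Section 3 neither repeats the 45-day criterion nor cites section 11. The only use of the count that the SAP writes down is the plot of loss by arm. The link to censoring is possible but unstated.
- **It has two conditions.** A participant must have had no contact and also have unknown vital status. Deaths are reported as they occur, and Appendix C has admissions and deaths collected through month 18. The SAP does not say whether a survivor between contacts counts as known to be alive. The master protocol body and the instruction manual, which might say so, are not among the documents.
- **A sound retention figure already exists.** Section 11 also reports expected and observed numbers of "participants with known vital status at days 5, 14, 28, 60 and 90, and at months 6, 12, and 18", and treats a visit as expected once its window has closed or its data have arrived. It would be wrong to say that retention cannot be judged after Day 90.
- **The reach is narrow.** The primary endpoint stops at Day 90 and has its own censoring rule in section 8.1. Efficacy, harm and later futility monitoring (sections 10.3 and 10.4) rest on it. In final analyses, a participant reached at months 6, 12 and 18 contributes follow-up to month 18 whatever the flag said in between.

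All four points stand, and they reduce this to a minor point. They do not remove the mismatch: the rule for expected visits is not applied to the loss count, and an unstated convention for vital status between contacts cannot be relied on to rescue the definition.

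**Conclusion.** The point holds as a minor defect. As written, the section 11 definition gives a wrong loss count after Day 90, covering about 71% of the time to month 18 for an on-schedule participant without interim contact or other vital-status information. On-schedule participants alone could trip the 10% example trigger.

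Any effect on estimates depends on section 3 using the same definition, which the SAP does not say. If it does, interim estimates of absolute mortality, and of re-admission or death, after Day 90 would be overstated. Under the assumed inputs the relative excess in mortality runs from zero to more than double. The base-case figures of about 19% and 45% differ only in how loss is dated, which the SAP also leaves open. These figures illustrate the mechanism and do not predict this trial's results.

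The primary endpoint, outcomes through Day 90, final analyses and the comparison between arms are essentially unaffected.

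**What to change.** 1. In section 11, limit the 45-day rule to follow-up through Day 90. After Day 90, count a participant as lost only when a month 6, 12 or 18 window (target day + 14) has closed with vital status at that visit unknown. This matches the rule for expected visits already in that section.
2. In section 3, state that this is the definition of loss to follow-up used for interim censoring, and give the date at which a lost participant is censored. Participants between windows then stay under the existing administrative-censoring rule.

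The cost is a sentence in each section and one changed derived variable. No new data are needed.

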12.1 Associations of Baseline Levels with Clinical Outcomes

For each treatment group, associations of baseline antibody status (negative versus positive), levels of plasma antigen, and levels of viral RNA at study entry, with time to *sustained recovery* through day 90 (primary efficacy outcome) and with important safety outcomes will be assessed.

12.2 Plasma Antigen Levels Through Day 5

Plasma antigen levels over time (Baseline, Days 1, 3, and 5) will be described using the following summary statistics, by treatment group, for all participants with follow-up data, and separately for participants who were nAb negative versus nAb positive at study entry:

• Number and percent of participants with antigen levels < 3 ng/L ("antigen negative"), and number and percent of participants with antigen levels < median antigen levels at

study entry (the cut-point used for subgroup analyses).

- Side-by-side box plots of antigen levels. Antigen levels < 3 ng/L (the lower limit of quantification) will be imputed as 2.9, and antigen levels will plotted on the log₁₀-scale.
- Geometric mean concentrations (GMC) of the antigen levels

Hypothesis 1: Over the first 5 days, antigen levels will decline faster in those receiving the investigational agent compared to those receiving placebo.

Hypothesis 2: The treatment effect (investigational agent versus placebo) on the antigen levels is stronger among participants who are nAb negative at study entry compared with those who are nAb positive at study entry.

To address these hypotheses, treatment groups will be compared for the percentage of participants who are antigen negative (i.e., antigen levels < 3 ng/L) at Days 1, 3, and 5, overall (Hypothesis 1) and within subgroups (Hypothesis 2).

- At each time point, the treatment difference will be estimated using a logistic regression model with the log₁₀-transformed baseline antigen level and disease severity indicator as covariates, and ORs with 95% CIs and p-values will be cited.
- In addition to the treatment comparisons at each time point (Days 1, 3, and 5), longitudinal GEE models will be fitted for the proportion of participants who are antigen negative over time, and slopes over time will be compared between treatment groups. The GEE models will be adjusted for baseline levels and disease severity.
- In addition to estimating the treatment differences within each subgroup, heterogeneity of the treatment effect across subgroups by baseline nAb status (Hypothesis 2) will be assessed by testing for an interaction between the treatment group indicator and the subgroup indicator for baseline nAb status in an expanded GEE model.
- Unadjusted analysis will also be performed, as sensitivity analysis.

Comment: Within the full study population, treatment comparison will be adjusted for nAb status at study entry by including the nAb status and disease severity indicators as covariates. Within nAb subgroups, comparisons will be adjusted for disease severity.

As secondary analyses, treatment groups will also be compared for the percentage of participants with antigen levels < median antigen level at study entry, as well as for the geometric mean concentration (GMC) of antigen levels.

In order to compare treatment groups for geometric mean concentration (GMC) of antigen levels, antigen levels < 3 ng/L will be imputed as 2.9 ng/L, and the treatment difference will be estimated as the GMC ratio for the investigational agent versus placebo. For this analysis, plasma antigen levels will be log₁₀-transformed, mean differences will be estimated with 95% Cls in ANCOVA models that include the treatment indicator as fixed effect and the baseline log₁₀ antigen level and disease severity indicator as covariates, and the treatment difference will be back-transformed to the original scale to estimate the GMC ratio. These analyses will be performed in the full study population, as well as within subgroups by nAb status. Heterogeneity of the treatment effect across subgroups will be assessed by testing for an interaction between treatment group and subgroup indicator in expanded ANCOVA models for the log₁₀-transformed antigen levels.

12.3 Antibody Levels Through Day 5

Levels of nAb and anti-N antibodies at baseline, Days 1, 3, and 5 will be described using the following summary statistics, by treatment group, for all participants with follow-up data, and separately within subgroups by antibody status (positive versus negative) at study entry. To investigate nAb levels over time, subgroups will be formed by nAb status. To investigate anti-N antibody levels over time, subgroups will be formed by anti-N antibody status. Similar analyses will be performed for anti-Spike IgG antibody levels.

- Number and percent of participants with nAb percent binding ratio
 > 30% ("nAb positive")
- Number and percent of participants with anti-Spike IgG antibody level
 > 770 ng/mL ("anti-Spike IgG positive")
- Side-by-side box plots of nAb, anti-N, and anti-Spike IgG antibody levels over time
- Median concentrations of the nAb, anti-N, and anti-Spike IgG antibody levels

Comment: The manufacturer of the anti-N antibody assay (BioRad) considers samples with specimen ratios < 0.8 as "antibody negative", and samples with values between 0.8 and 1 as "equivocal". For our analyses, we refer to all samples with specimen ratio < 1 as "anti-N negative".

Treatment groups will be compared for the following outcomes, overall and within subgroups by antibody status at study entry:

- The percentage of participants who are nAb positive (i.e., percent binding ratio
 > 30%) at Days 1, 3, and 5, overall and within subgroups by nAb status at study entry.
- The percentage of participants who are anti-N antibody positive (i.e., specimen ratio 1) at Days 1, 3, and 5, overall and within subgroups by anti-N antibody status at study entry.
- The percentage of participants who are anti-Spike IgG antibody positive (i.e., antibody level
 > 770 ng/mL) at study entry at Days 1, 3, and 5, overall and within subgroups by anti-spike IgG antibody levels at study entry.

Statistical methods are similar to those described for comparing antigen levels over time.

In addition, at Days 1, 3, and 5, treatment groups will be compared for mean antibody levels (nAb, anti-N, and anti-Spike IgG levels), and the mean difference (investigational agent minus placebo) will be estimated with 95% CIs, overall and in subgroups by antibody status, using ANCOVA models that include the treatment indicator as fixed effect, and the baseline antibody level (continuous covariate) and disease severity indicator as covariates. Treatment groups will also be compared for mean change over time using longitudinal mixed effects models, comparing slopes of mean antibody levels over time between treatment groups. Heterogeneity of the treatment effect across subgroups will be assessed by testing for an interaction between treatment group and subgroup indicator in expanded longitudinal mixed effects models.

Comment: The analyses of mean levels of nAb and anti-N antibody levels are exploratory, as the assays are qualitative. In contrast, the anti-Spike IgG antibody assay is semi-quantitative, and for that assay percentiles will be considered in subgroup analyses as well as classification of results as antibody negative/positive.

13 Exploratory Analyses

